# 4.6 Criteria for withdrawal of participants

Participants can withdraw their consent from the study at any time.

#### 5.0 Study Design

The study is a prospective observational study evaluating treatment outcomes and diagnostic testing methodology in a cohort of HIV-HCV coinfected individuals undergoing standard DAA (initially SOF/DAC) treatment delivery in the hospital outpatient setting in Myanmar. Since this is an observational cohort there is no formal sample size calculation. All patients commencing DAA therapy who agree to be enrolled during the period of the study will be included.

[figure not shown]

Fig 1. Schema for non-cirrhotic patients (treatment duration for decompensated cirrhotic patients 24 weeks) \*via fingerstick testing

# **6.0** Study Procedures

#### 6.1 Standard of care

Serological screening for viral hepatitis infection is now routinely done at both Specialist Hospitals Mingaladon and Waibargi. Those who tested positive for anti-HCV antibody by WHO pre-qualified test kit (SD Bioline) and who meet the treatment eligible criteria by "Simplified Treatment Guideline for HCV Infection, Myanmar" (i.e. normal renal function, not pregnant, older than 18 years and not taking anti-TB drugs), will be given an appointment (first visit of HCV care). On that day, 10 ml of blood (6 ml for RNA, 1 ml for CBC and 3 ml for biochemistry) will be drawn for testing HCV RNA and other baseline tests. Three millilitres of plasma will be put in ice-box and sent to National Health Laboratory on the same day to test HCV RNA by GeneXpert 4 module machine. Baseline investigations are complete blood count (CBC), serum creatinine, ALT and ultrasound of the abdomen.

All patients will be given one week's appointment to enquire results (second visit of HCV care). Those with detectable HCV viral load (> 10 IU/ml) are offered DAA (Direct Acting Antivirals: sofosbuvir + dose adjusted daclatasvir). APRI score (ALT platelet ration index) is calculated. Significant fibrosis is defined as clinical cirrhosis with signs of chronic liver insufficiency and ascites, or fibrosis/cirrhosis on ultrasonography, or APRI score >2. The duration of treatment is 12 weeks for non-cirrhosis and 24 weeks for cirrhosis. Drugs are to be picked up monthly. Cure is determined by undetectable HCV RNA 12 weeks after completion of treatment.

#### 6.2 Research

The study entry point to research will be the day when blood is collected by the program. Before blood collection, those who met the inclusion criteria will be interviewed by the investigator/research assistant and explained about the nature of research and invited to participate. After obtaining written informed consent, they will be asked to fill a demographic screening form (Behavioural Screening Questionnaire). Study staff will be available to assist participants to complete this questionnaire as required.

The investigator or research MO will collect information on HCV RNA, fibrosis state of the liver, CD4 counts, renal function and HCV medication (Pre-treatment Clinical Assessment).

Then 15 ml of venepuncture blood (10 ml for standard of care and extra 5 ml for research) and a single fingerstick blood will be collected (i) on GeneXpert cartridge (a variant cartridge that can run on fingerstick samples) and (ii) 4 or 5 blood drops will be put on dried blood spot cards, air-dried, transferred to -20°C and batch shipped to VHCRP at Kirby Institute at the close of

the study. Five ml of whole blood will be immediately centrifuged at SHM laboratory to give rise to about 2.5 ml of plasma which is transferred to Common Research Laboratory of UM 2 on the same day to be stored there at -70°C until batch-shipped to Kirby Institute, Australia. In VHCRP lab DBS will be analysed for HCV core antigen and HCV RNA by Abbott M2000/Architect machine.

All patients will undergo a second interview and clinical assessment 12 weeks after completion of HCV treatment. This includes all facts collected in the Pre-treatment clinical assessment plus major side effects the patients suffered (Post-treatment clinical assessment).

Participants will undergo the following testing as per the schedule of assessments

**Table 1. Scheduled assessments** 

Assessment / Procedure	Screening/baseline	Follow-up
Study weeks	-6 to 0	24 (SVR12)
Informed consent, medical history, risk	Х	
behaviour		
Liver function tests/ Full blood count/	Х	Х
eGFR		
HIV RNA/ CD4 count	x	Х
HCV-RNA testing (NHL) (Xpert®)	Х	Х
Finger stick capillary blood (Xpert®) a	Х	Х
Plasma store for HCV RNA b (Abbott)	Х	Х
Dried blood spot c (Abbott/Architect)	Х	Х

NHL = National Reference Laboratory

<sup>a Capillary blood collected by fingerstick and transferred to UM2 laboratory for HCV RNA testing using GeneXpert machine

<sup>b A single plasma store will be collected and stored at -70°C for HCV RNA testing, plus future immunovirological research as allowed including HBV validation

<sup>c Fingerstick capillary blood air dried on filter paper and temporarily stored at -20°C at Mingaladon, then sent to Kirby Institute for HCV and HBV testing and future immunovirological research

# 6.3 Virological testing

The following virological methodology will be employed:

- 1. Standard Plasma HCV RNA testing
  - a. Myanmar

A plasma sample will be taken pre-treatment initiation to confirm active HCV viremia before commencement of therapy. This sample will be sent to the National Health Laboratory in Yangon for testing as per the Myanmar HCV treatment guidelines. Current testing is with the GeneXpert technology (module 4).

b. International

A single HCV RNA plasma store will be collected and stored at -70°C and batch shipped to VHCRP at Kirby Institute at the close of the study. The sample will be analysed for HCV RNA by Abbott M2000 RT machine, as an international standard to cross-validate DBS and local lab result.

- 2. Finger stick capillary blood sample (research).
  - A sample of whole blood will be collected via finger-stick for a HCV point of care test. This sample will be used to test HCV viral load via the Xpert® HCV Assay performed on the GeneXpert instrument system at the research laboratory. This test uses reverse transcriptase polymerase chain reaction (RT-PCR) and provides a measure of HCV RNA levels within 60 minutes.
- 3. Dried blood spot collection (DBS) for HCV core antigen and HCV RNA testing (research).

A finger-stick whole-blood sample will be collected for the dried blood spot sample collection using a (MiniCollect Safety Lancet; Greiner Bio-One, Monroe, Frickenhausen, German). Five spots (depending on available blood) of capillary whole-blood collected by finger-stick will be collected on dried blood spot cards, airdried, transferred to -20°C and batch shipped to VHCRP at Kirby Institute at the close of the study. In VHCRP lab DBS will be analysed for the presence of HCV, including HCV core antigen and HCV RNA.

Participants will not receive the results of any of the research samples as these are not accredited assays.

[figure not shown]

Fig 2. Diagnostic methods to be used

# 6.4 Methodology for Dried Blood Spot testing

HCV RNA testing using Abbott RealTime HCV Viral Load assay (Abbott Molecular, Illinois, United States) and HCV core antigen testing using the ARCHITECT HCV Ag will also be performed on dried blood spot as per manufacturer protocols. HBV will also be tested on dried blood spots as per manufacturers' protocols. Briefly, DBS spots will eluted in buffer, agitated by rotation for one hour at room temperature, centrifuged and analysed on the Abbott M2000RT Realtime PCR instrument, according to manufacturer's directions.

#### 6.5 Sample transportation and storage

Some biological samples may eventually be transported to and stored at Kirby Institute. All staff that will be handling, packaging and/or transporting biological samples will be appropriately trained and will follow the correct sample collection and handling procedures.

#### 6.6 Laboratory investigations

DBS samples and whole blood POC sample will be used for central lab HCV RNA testing. The DBS sample will be analysed to test for the presence of the hepatitis C virus, including HCV RNA. The sample will also be analysed to determine the genetic sequence of the HCV virus, which will then be assessed using phylogenetics, to compare it to other HCV sequences. The samples will be evaluated to explore potential transmission patterns among this population.

# 6.6.1 Whole blood in GeneXpert cartridge

GeneXpert machine to run on this sample is housed at Common Research Laboratory (CRL), University of Medicine 2. Whole blood obtained from fingerstick will be directly placed on GeneXpert cartridge, which will then be transported the CRL on the same day in ice-box. At the CRL, the sample will be tested on the same day or immediate next day. The samples will not be stored. The sample-containing cartridge will be discarded according to the laboratory's infection protocol.

# 6.6.2 Dried Blood Sample

Dried blood spot specimens will be collected by applying a few drops of blood, drawn by lancet from the finger, onto an absorbent filter paper. The blood is allowed to thoroughly saturate the paper and is air dried for a few hours. Specimens will be transferred into plastic bags with desiccant added to reduce humidity. These samples will be stored at -20°C at CRL and batch-shipped to VHCRP at Kirby Institute at the close of the study. In VHCRP lab DBS will be analysed for the presence of HCV, including HCV core antigen and HCV RNA. The samples will not be stored at VHCRP. After analysis, the samples will be discarded.

#### 6.6.3 Plasma

About 5 milliliters of venepunctured blood is centrifuged to give rise to 2.5 ml of plasma at site laboratory and transported to CRL in an ice-box on the same day. The samples will be stored at -70°C in the freezer and batch-shipped to VHCRP laboratory in Sydney, Australia. The plasma samples will be stored for 2 years after completion of the study. If no continuation study arises, the samples will be destroyed. If a continuation study arises, the proposal will be submitted to ITERB of UOPH.

#### **6.7 Questionnaires**

All participants will complete a questionnaire at baseline and at SVR12. Questionnaires will be completed on paper or electronically on tablet. Study staff will be available to assist participants to complete this questionnaire as required.

## a) The Behavioral Questionnaire

The behavioral survey will collect information on the following:

- Demographics
- Injecting and alcohol
- Drug treatment history
- Hepatitis C testing and treatment knowledge
- Quality of life

#### 6.8 Clinical assessment

The clinic nurse or physician will assess the participant's medical history and known or likely liver disease related conditions. They will collect a sample of blood for routine clinical analysis. The pathology tests taken under the clinical assessment will not be regulated through this study. It is up to the study nurse or physician to decide on which tests are collected, based upon routine standard of care. These tests are part of normal standard of care practice.

## 7.0 Endpoints

## 7.1 Primary endpoint

 Proportion of patients achieving SVR 12 (HCV RNA < LLD at least 12 weeks post therapy completion)

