## 3.0 Objectives

## 3.1 Primary objective

To evaluate the proportion of patients with undetectable HCV RNA at 12 weeks post-treatment (SVR12) following a course of DAA therapy delivered using a simplified schedule of safety and virological monitoring.

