## 7.4 Statistical methodology

Descriptive analyses will be performed to characterise the study population including median (interquartile range) or mean (SD). Patient population will be described by age, sexual orientation, education, income, liver disease stage (categorised by APRI), drug and alcohol use, daily functioning and HIV parameters as well as HCV related parameters including HCV genotype and viral load. Continuous variables will be summarised by either mean and standard deviation (SD) or median and interquartile range (IQR), as appropriate.

Factors associated with knowledge of liver disease will be assessed using logistic regression analyses. Variables hypothesized to be associated with HCV knowledge to be assessed in unadjusted analyses will include: sex, age, education, accommodation, employment, social functioning, injecting drug use, alcohol use and HCV infection status. All variables with p<0.20 in bivariate analysis will be considered in multivariate logistic regression models using a backwards stepwise approach sequentially eliminated subject to the result of a likelihood ratio test. Statistically significant differences will be assessed at p<0.05 (two-sided p-values).

Proportion of participants achieving SVR will be calculated. SVR12 will be defined as HCV RNA target not detected (TND) or target detected, not quantifiable (TD, nq) at post-treatment week 12. For the efficacy endpoint, means and proportions with two-sided 95% confidence intervals (CI) will be determined. Categorical data will be analysed using the Chi squared or Fisher's exact test. Continuous variables will be analysed using the t-test or the Mann-Whitney U test, as appropriate.

Logistic regression analysis will be used to identify factors associated with SVR. Potential predictors will be determined *a priori* and will include age, gender, liver disease stage (categorised by APRI), drug use and alcohol use, CD4 count and HIV RNA.

The multivariate models will be determined using a backwards stepwise approach, considering factors that were significant at the 0.2 level in univariate analysis. The final models will include factors that remain significant at the 0.05 level. All statistical tests will be two-sided with a significance level of 0.05. Analysis will be performed using STATA (version 14.0; Stata Corporation, College Station, TX).

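### Sections 7.1 and 7.4 define the primary endpoint differently, in both timing and HCV RNA threshold, so the same patient can be SVR12 under one and not under the other

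*Protocol*

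**What the plan says.** Section 7.1 gives the primary endpoint as the proportion with "HCV RNA < LLD at least 12 weeks post therapy completion". Section 7.4 defines SVR12 as "HCV RNA target not detected (TND) or target detected, not quantifiable (TD, nq) at post-treatment week 12".

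The other sections do not settle the matter:
- Section 3.1 states the objective as undetectable RNA twelve weeks after treatment.
- Section 6.1 says "Cure is determined by undetectable HCV RNA 12 weeks after completion of treatment".
- Section 6.2 says "All patients will undergo a second interview and clinical assessment 12 weeks after completion of HCV treatment", with no tolerance.
- Table 1 has one follow-up column, at study week 24, with no window.

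Three further facts bear on the remedy. Section 6.6 plans sequencing on the dried blood spot (DBS) sample: "The sample will also be analysed to determine the genetic sequence of the HCV virus". Its stated use is phylogenetics and transmission patterns. Table 1 schedules DBS at both visits, and section 6.6.2 says the samples are discarded after analysis. The candidate predictors of SVR in section 7.4 include "liver disease stage (categorised by APRI), drug use and alcohol use, CD4 count and HIV RNA".

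**The concern.** This is the primary endpoint, and the protocol gives two rules for it. An analyst following 7.1 and one following 7.4 could report different numerators, or different denominators, from the same data. A later SAP would have to overrule one section.

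The open end in 7.1 has a second consequence. A patient with quantifiable RNA meets neither definition, so virus acquired after cure counts as non-SVR by implication, and the longer the interval before the test, the more time there is for that to happen. Drug use is a candidate predictor of SVR and could be linked to re-exposure. The protocol does not mention reinfection.

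**Working it through.** **1. The definitions side by side**

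| Source | Timing | Threshold |
|---|---|---|
| 3.1 | 12 weeks after treatment | undetectable |
| 6.1 | 12 weeks after treatment | undetectable |
| 7.1 | 12 weeks or any later time | below LLD |
| 7.4 | post-treatment week 12 | not detected, or detected and not quantifiable |

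The objective agrees with 7.4 on timing and with 7.1 on threshold, so neither section can simply be taken as the correct one. The protocol does not spell out LLD. Read as a limit of detection, it need not be met by a result reported as detected.

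Two patients show the conflict. One is first tested 30 weeks after treatment with no virus detected: SVR under 7.1, no qualifying result under 7.4. The other is tested exactly at week 12 with a detected, unquantifiable result: SVR under 7.4, and possibly not under 7.1 or 3.1.

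Table 1 does not help. Study week 24 is post-treatment week 12 only after a 12-week course (12 + 12 = 24). After the 24-week course also described in section 6.1 it would be week 36 (24 + 12).

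**2. The plan's own figure**

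Section 7.3 gives 91-98% around 95% for 200 patients. The exact (Clopper-Pearson) interval for 190/200 is 91.0-97.6%, which rounds to that. The figure is for sensitivity and specificity, and the endpoint conflict does not change it. The same interval describes the precision of an SVR12 of 95% in 200 patients.

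**3. What reclassification does to SVR12**

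One patient is 1/200 = 0.5 points. Start from 190/200 = 95.0% under 7.1 and suppose *m* of the 190 successes were tested late. The values of *m* are assumptions; the protocol gives none.

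| *m* | 7.4, late results excluded | 7.4, late results scored non-SVR |
|---|---|---|
| 2 | 188/198 = 94.9% | 188/200 = 94.0% |
| 10 | 180/190 = 94.7% | 180/200 = 90.0% |
| 20 | 170/180 = 94.4% | 170/200 = 85.0% |

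In this setting the conflict costs little if late results are excluded and much more if they are scored non-SVR. Each detected, unquantifiable result moves the estimate by 0.5 points in the same way. The denominator may be below 200, because section 6.2 enrols before the RNA result is known and section 6.1 offers treatment only to those with detectable RNA. Each patient would then weigh slightly more.

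**4. Reinfection, as illustration only**

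Assume true cure of 95%, a share *s* of 10-50% exposed through drug use, a reinfection rate *r* of 2-20 per 100 person-years in that group, and every patient tested *t* weeks after treatment. Expected reinfections scored non-SVR = 200 x 0.95 x *s* x [1 - exp(-(*r*/100) x *t*/52)]. For example, *s* = 0.3, *r* = 5 and *t* = 12 give 200 x 0.95 x 0.3 x 0.0115 = 0.65 patients and an observed SVR of 94.7%. The odds ratio for non-SVR with drug use, when true cure is equal, is then 1.23.

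| Test at week | Reinfections among 200 | Observed SVR | Odds ratio for drug use |
|---|---|---|---|
| 12 | 0.1-4.3 | 95.0-92.9% | 1.1-1.9 |
| 24 | 0.2-8.4 | 94.9-90.8% | 1.2-2.9 |
| 52 | 0.4-17.2 | 94.8-86.4% | 1.4-5.4 |

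None of *s*, *r* or *t* comes from the protocol, apart from the scheduled week 12.

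**The case against.** The strongest reply is that the timing gap is only loose wording. Sections 3.1, 6.1, 6.2 and 7.4 all say 12 weeks, Table 1 has a single follow-up visit, and 7.1 can be read as setting the earliest date for it. No later test is planned, so late results arise only from delayed visits, and visit windows are often left to an SAP. This limits the likely number of patients affected. It does not remove the conflict, because the protocol states two rules and not merely an incomplete one. It also leaves the threshold difference, which applies even to a test done on time.

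A reader might infer more: that late virus is wrongly counted as treatment failure, and that SVR12 and the drug-use association are therefore biased. The documents do not support that.
- Against the stated objective, any viraemia at the test is non-SVR. Separating reinfection answers a supplementary question and does not correct the endpoint.
- Section 7.4 seeks factors associated with SVR; it does not claim to isolate drug response.
- The rates, exposed share and delays are all assumed. The week-52 row needs the whole cohort tested a year late. If the two years in section 4.5 include follow-up, 12 weeks of treatment plus 52 of delay leave only patients enrolled in the first 104 - 64 = 40 weeks.
- Rules for classifying reinfection may sit in an SAP that is not at hand, so their absence is no error.

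What remains is practical: the sequencing is planned anyway, and the samples are not kept afterwards.

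**Conclusion.** The primary endpoint is defined inconsistently in timing and threshold, and nothing else in the protocol resolves it. This should be corrected. The effect is 0.5 points of SVR12 per reclassified patient at N = 200. The total depends on how many patients return late or have a detected, unquantifiable result, and on how out-of-window results are scored; the protocol states none of these.

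Bias from reinfection is possible but not shown. Under the assumed ranges above, the loss at the scheduled week 12 runs from under 0.1 to about 2 points, against an exact interval of 91.0-97.6% around 95%. It grows only if testing is much delayed. That part supports a sensitivity analysis and no change to the primary one.

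**What to change.** - Put one definition in 7.1 and 7.4, and align 3.1 with it: one threshold with LLD spelled out, and a stated window that starts 12 weeks after the last dose and has an upper limit. Counting from the last dose also covers the longer courses that Table 1 does not fit.
- State how results outside the window and missing results are scored. Add a sensitivity analysis that includes late results, since late return may itself be related to drug use.
- Keep all viraemia as non-SVR in the primary analysis.
- Specify in advance that baseline and SVR12 sequences are compared in patients viraemic at SVR12. At the 95% SVR assumed in 7.3 that is about 200 x 0.05 = 10 patients at most. Use the DBS pairs: section 6.6 assigns sequencing to DBS, whereas SVR12 plasma is uncertain (section 4.0 limits that visit to fingerstick, Table 1 lists stored plasma). Arrange this before the samples are discarded.
- As a sensitivity analysis, report SVR12 and the whole predictor model with sequence-proven reinfection separated from relapse or non-response. The outcome should change for the whole model, not for drug use alone.

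The cost is a wording change and a small number of sequence comparisons in samples already due for sequencing. The downside is that a few late returners leave the main window.

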# 7.2 Secondary endpoints

- Sensitivity and specificity of HCV RNA on GeneXpert machine using capillary blood collected via fingerstick compared to standard HCV RNA plasma tests
- Sensitivity and specificity of HCV RNA on DBS compared to standard HCV RNA plasma tests
- Sensitivity and specificity of HCV core antigen on DBS compared to standard HCV RNA plasma tests
- Proportion of patients identified with active HCV viremia at screening
- Change in HIV RNA/T cell count pre and post therapy
- Change in liver function tests and APRI score pre and post therapy
- Knowledge of the patients on HCV testing and treatment

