However, major challenges still remain, particularly around the simplification of diagnostic and testing methodology . Currently, the HCV testing algorithm involves the detection of HCV antibodies to confirm exposure followed by HCV RNA or core antigen testing to detect active infection. This two-step process to confirm active infection requires multiple visits and results in a loss of patients diagnosed with HCV infection. In addition to multiple visits, HCV RNA determination (qualitative or quantitative) requires the collection and preparation of plasma in a standardised laboratory, with resultant significant expense and complexity, providing a major barrier to testing in many situations. Point-of-care HCV testing using oral fluid and fingerstick capillary blood rapid diagnostic testing has been shown to increase testing and linkage to care 6-10 However, many currently available point-of-care tests only measure HCV antibodies, not HCV RNA. More recently the development of rapid point-of-care (POC) tests to enable HCV RNA detection in the clinic (e.g. Xpert® HCV Viral Load, Cepheid®) has shown potential for implementation. Currently, the only two CE-marked point-of-care HCV RNA assays (the Xpert® HCV Viral Load, Cepheid and the Genedrive® HCV ID Kit, Genedrive) both require venepuncture, which is challenging in settings without access to phlebotomists or among people with poor venous access, including people who inject drugs 13. Further

improvements to this technology have demonstrated HCV RNA can also be detected in fingerstick capillary blood (Grebely Lancet Gastro 2017, and Lamoury under review).

Methodology involving the collection and testing of dried blood spot (DBS) for HCV RNA and/or HCV core antigen has further potential for significantly upscaling testing by simplifying linkage from the clinic through to treatment and care. Although showing great promise these new technologies require validation against the current gold standard of plasma HCV RNA quantification, both in resource rich and resource limited settings.

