# 2.0 Hypotheses

- Simplified virological and safety monitoring during and following DAA therapy is an effective and safe management strategy in a resource limited setting
- Novel diagnostic methods for HCV detection including DBS collection and fingerstick capillary HCV RNA testing (GeneXpert, Cepheid) will perform in an equivalent manner to standard plasma HCV RNA methodology

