#### 3.2 Secondary objectives

- 1) To evaluate acceptability and feasibility of DBS collection in Myanmar.
- 2) To evaluate concordance pre and post therapy between HCV RNA (fingerstick) and standard plasma HCV RNA detections.
- 3) To evaluate concordance pre and post therapy between HCV core antigen (DBS) and standard plasma HCV RNA detections.
- 4) To evaluate concordance pre and post therapy between HCV RNA (DBS) and standard plasma HCV RNA detections.
- 5) To evaluate patients' knowledge on HCV by using set-up questionnaire.
- 6) To understand HCV virus patterns in Myanmar through phylogenetic sequencing.
- 7) To enhance and develop laboratory and research capacity at Specialist Hospital Mingaladon (SHM), Specialist Hospital Waibargi (SHW) and Insein General Hospital (IGH).

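### Fingerstick and DBS HCV RNA are assessed only as detected or not detected; the viral loads from the same assays would test the equivalence hypothesis better at almost no cost

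*Protocol*

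**What the plan says.** Protocol section 7.2 lists one kind of performance measure for each new test. For DBS RNA it is "Sensitivity and specificity of HCV RNA on DBS compared to standard HCV RNA plasma tests". For fingerstick RNA it is "Sensitivity and specificity of HCV RNA on GeneXpert machine using capillary blood collected via fingerstick compared to standard HCV RNA plasma tests". DBS core antigen is treated likewise. Section 7.4 mentions viral load only as a descriptor of the population.

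The RNA assays give numbers. Section 6.3 says that the fingerstick Xpert test "provides a measure of HCV RNA levels within 60 minutes". Section 6.4 specifies "HCV RNA testing using Abbott RealTime HCV Viral Load assay" for the DBS. Section 6.3 also provides two plasma results: Xpert at the National Health Laboratory (NHL), and Abbott on stored plasma as an international standard.

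On purpose, section 1.0 says that "these new technologies require validation against the current gold standard of plasma HCV RNA quantification", and hypothesis 2 in section 2.0 says that the new methods "will perform in an equivalent manner to standard plasma HCV RNA methodology". That hypothesis is about methods for HCV detection. The matching objective in section 3.2 is "To evaluate concordance pre and post therapy between HCV RNA (DBS) and standard plasma HCV RNA detections".

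Section 7.3 assumes SVR 95% and sensitivity and specificity of 95%. It counts baseline and SVR12 samples together (200 patients, 400 samples) and gives a 95% CI of 91-98%.

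**The concern.** Almost every positive sample in this study will come from an untreated patient. If those patients have high viral loads, a yes/no result on them is easy to get right, and sensitivity says little about signal lost through small volume, elution or storage. The few positives after treatment are too few to settle the matter and carry little weight in a pooled figure.

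A sample type could therefore be reported as equivalent to plasma although it reads systematically low, or although it fails in the small group where it would be used to find treatment failure. The paired baseline viral loads would show a systematic loss with good precision, but no listed endpoint uses them.

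**Working it through.** **1. The plan's own interval.** Exact (Clopper-Pearson) 95% CI for an observed 95%, taking about one class per visit (baseline positive, SVR12 negative):

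| n in class | Exact 95% CI | Section 7.3 |
|---|---|---|
| 100 | 88.7-98.4% | 89-98% |
| 150 | 90.2-97.9% | 90-98% |
| 200 | 91.0-97.6% | 91-98% |

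The stated intervals are reproduced and are not in dispute.

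**2. Where the positives come from.** Inputs from section 7.3: 200 patients, one sample at baseline and one at SVR12, SVR 95%. Added assumption: all baseline samples are viraemic and all patients are tested at both visits.
- Baseline positives: 200.
- SVR12 positives: 200 x 0.05 = 10.
- Total positives: 210, of which 200/210 = 95.2% are from baseline.

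**3. A test that detects every baseline positive and no SVR12 positive.** Pooled sensitivity = 200/210 = 95.2%, exact 95% CI 91.4-97.7%. That meets the planning figure of 95% with CI 91-98%.

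**4. SVR12 alone.** If all 10 were detected, the exact 95% CI for 10/10 is 69-100%. Separate reporting would expose the failure in step 3, but it cannot show good performance at SVR12 with any precision.

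**5. Would baseline sensitivity show a tenfold under-reading?** The protocol gives no viral-load distribution and no detection limit for the new sample types, so these are assumptions. Take log10 load as normal with mean m and SD s, detection limit L (log10 IU/ml) and loss d. Then sensitivity = Phi((m - d - L)/s).

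| m | s | L | No loss (d = 0) | Tenfold loss (d = 1) |
|---|---|---|---|---|
| 6.0 | 0.8 | 2.5 | 100.0% | Phi(3.125) = 99.9% |
| 6.0 | 0.8 | 3.0 | 99.99% | Phi(2.5) = 99.4% |
| 5.7 | 1.0 | 3.5 | Phi(2.2) = 98.6% | Phi(1.2) = 88.5% |

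Over m 5.7-6.0, s 0.8-1.0 and L 2.5-3.5, a tenfold loss gives 88.5-99.9%.
- Middle row: about 199/200 (exact CI 97.2-100%) against 200/200 with no loss (98.2-100%). The two cannot be told apart.
- Bottom row: 177/200 has an exact CI of 83.2-92.6%, which excludes 95%. The loss would be seen.

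**6. What the paired values would show.** The half-width of the 95% CI for the mean log10 difference with 200 pairs is 1.96 x SD/sqrt(200). The SD of differences is assumed, since the protocol gives none.
- SD 0.3: 0.04 log10
- SD 0.5: 0.07 log10
- SD 0.7: 0.10 log10

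A shift of 1 log10 would be plain at any of these.

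**The case against.** The strongest reply is that the endpoints match the objectives. Section 3.2 asks for concordance of detections, hypothesis 2 is about detection, and the care pathway in section 6.1 uses the result as yes or no: "Those with detectable HCV viral load (> 10 IU/ml) are offered DAA", with undetectable RNA defining cure. A two-by-two table is a proper summary of that. This stands. A reader might infer from the word quantification in section 1.0 that the protocol demands quantitative agreement and then fails to plan it. The text does not support this: the sentence is background, can be read as naming the reference test, and also covers core antigen, which is not measured in IU/ml.

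A reader might also infer that baseline sensitivity is always blind to signal loss. Step 5 shows that it is not: with a high detection limit and lower loads the loss is visible. Nor does the protocol say that treatment failures at SVR12 have low viral loads, and a constant offset in reported IU/ml need not mean missed positives.

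Agreement statistics are often left to an analysis plan, which is not at hand, so their absence from section 7.4 is not in itself a fault. The measures by which the tests are judged are nevertheless fixed in section 7.2, and the 200/210 result follows from section 7.3 without any assumption about viral load. Pooling across visits is implied by the sample count in section 7.3 but is not stated as the analysis.

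**Conclusion.** The point holds as a worthwhile improvement at almost no cost. It is not an inconsistency in the protocol, and the stated precision of 91-98% is correct.

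The firm part is that about 200 of 210 expected positives are baseline samples, so pooled sensitivity of 95.2% is compatible with missing every SVR12 positive. This rests on SVR 95%, complete sampling and universal viraemia at baseline. The last is generous: entry requires HCV antibody, consent precedes the RNA result, and the proportion viraemic is itself an endpoint. Fewer viraemic patients would reduce both the baseline positives and the number of usable pairs.

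The conditional part is that a tenfold under-reading may go unseen in baseline sensitivity. Under the assumed inputs it would show as anything from 88.5% to 99.9%, and the protocol supplies none of those inputs.

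**What to change.** In sections 7.2 and 7.4:

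1. Report sensitivity and specificity separately for baseline and SVR12.
2. Report sensitivity by plasma viral-load band for all index tests, including core antigen.
3. For the two RNA tests at baseline, add the mean paired difference in log10 IU/ml with its 95% CI and Bland-Altman limits of agreement. Compare DBS Abbott with plasma Abbott, and fingerstick Xpert with NHL plasma Xpert, so that a platform offset is not mistaken for loss due to sample type.
4. Report how many plasma-positive pairs are not quantifiable on the index test, and add a sensitivity analysis that treats them as censored at the index limit. Restricting to pairs quantifiable on both would drop the samples that the new test misses and could bias the mean loss towards zero.
5. Interpret hypothesis 2 for the RNA tests on these results together with sensitivity and specificity, or state that the validation covers detection only.

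The cost is a few more lines of analysis and results, with no new samples or assays. Sections 6.3, 6.6 and 6.6.2 describe DBS testing as showing the presence of virus, so confirm that the numeric DBS result will be recorded.
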